## 9 Statistical design and analysis

Sample size is driven by the difference in APHAB global benefit scores between self-fitting and the professionally-fitted hearing aid. Assuming that the average difference score,  $APHAB_{self} - APHAB_{prof}$  is -5.0, and the standard deviation of the difference score is 14, 40 subjects with APHAB global scores in both periods are needed to demonstrate with 90% power the non-inferiority against the margin of -12.5 using Mixed Model ANOVA, setting one-tailed  $\alpha=0.025$ .

Anticipating an attrition rate of no more than 10%, to minimize the impact of imputed data on the overall efficacy conclusion, 44 subjects will be enrolled and those randomized will enter into the Intent to Treat population.

In terms of examining safety, the proportion of subjects experiencing any Adverse Device Effect will be a key safety endpoint. A sample size of 40 provides a 95% Clopper-Pearson confidence interval with a half-width no wider than 0.133 when the observed sample proportion is 0.20 or less. In other words, we can be 95% confident that the true population proportion of Adverse Device Effects is no greater than 0.133 larger than the observed sample proportion when the sample size is 40 and the sample proportion is 0.20 or less.

Note that this sample size is slightly higher than that included in 510(k) K213424, which included the same endpoints and a similar crossover design.

The analysis populations are as follows:

Intent to Treat: All participants randomized.

Safety: All participants randomized who receive one or more study device kits.

Data will be entered immediately following participant completion of the assigned tasks. Unaided and both aided responses will be analyzed for each participant for the APHAB global benefit and dB SNR loss scores. The two aided conditions will be analyzed for non-inferiority as per the statistical plan.

The APHAB global benefit score recorded during the self-fitting will be compared to the APHAB global benefit score recorded during the professional-fitting by way of a 2-period, crossover, repeated measures mixed model, where APHAB score is the dependent variable, treatment sequence is the between-subjects factor, Period is the within-subjects factor and treatment (Self-Fit/Professional-Fit) is the repeated measures factor.

The hypotheses are:  $H_0: \mu_{\text{self}} - \mu_{\text{prof}} < -12.5$   $H_a: \mu_{\text{self}} - \mu_{\text{prof}} \geq -12.5$ ,

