where  $\mu_{\text{self}}$  represents the mean APHABself score in the population and  $\mu_{\text{prof}}$  represents the mean APHABprof score in the population.

The observed treatment effect will be compared to the non-inferiority margin of -12.5 by way of pre-planned TEST or ESTIMATE statements using SAS PROC GLM or PROC MIXED.

The carryover effect will be tested by means of a RANDOM statement on the subject nested within sequence effect.

The planned analysis will be done by an expert biostatistician who has previous experience with FDA clinical trials.

The dB SNR loss score recorded during the self-fitting will be compared to the dB SNR loss score recorded during the professional fitting by way of a 2-period, crossover, repeated measures mixed model, where dB SNR loss score is the dependent variable, treatment sequence is the between-subjects factor, Period is the within-subjects factor and treatment (Self-fit/Professional-Fit) is the repeated measures factor.

The carryover effect will be tested by means of a RANDOM statement on the subject nested within sequence effect.

All analyses will be completed by an expert biostatistician who has previous experience with FDA clinical trials.

At each return lab visit, the sub-investigator A will notate any device deficiencies or possible adverse events as reported by the participant in the participant study folder.

If any AE are reported, the severity and scope will be reviewed and the study manager/sponsor, along with the PI will decide on the appropriate follow up.

Treatment-emergent Adverse Events will be attributed to the treatment condition (self-fit or professional fit) of the device being evaluated. The number and proportion of subjects reporting any Adverse Event, any Adverse Device Effect, any Serious Adverse Event, or any Serious Adverse Device Effect will be summarized by treatment condition and overall. The incidence of Adverse Events by AE term will be summarized by treatment condition and overall.

Missing aided APHAB global benefit scores and dB SNR loss scores for either visit 3 or 4 will be subjected to multiple imputation. Originally, missing data is assumed to be monotone and Missing at Random (MAR). Multiple imputation approach will follow fully-conditional specifica-

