tion, Multiple Imputation of Chained Equations. There will be a minimum of 100 iterations of missing data, and these iterations will be combined according to Rubin's (1987) rules. Sensitivity analysis of the MAR assumption will be based on pattern-mixture model (Molenberghs and Kenward, 2007)

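### If any aided score is missing, pooling by Rubin's 1987 rules without small-sample degrees of freedom puts the one-sided 0.025 test at roughly 0.026 to 0.029

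*Combined protocol and SAP*

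**What the plan says.** All the relevant text is in section 9 (Statistical design and analysis) of the combined protocol and SAP.

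- **Sample size.** The expected self-minus-professional difference in APHAB global benefit "is -5.0, and the standard deviation of the difference score is 14". From this the plan concludes that "40 subjects with APHAB global scores in both periods are needed to demonstrate with 90% power", at one-tailed alpha 0.025 and a margin of -12.5. It allows for up to 10% attrition and states that "44 subjects will be enrolled and those randomized will enter into the Intent to Treat population".
- **Test.** The treatment effect is compared with the margin through "pre-planned TEST or ESTIMATE statements using SAS PROC GLM or PROC MIXED". No df method is named.
- **Missing data.** Aided APHAB and dB SNR loss scores missing at visit 3 or 4 are multiply imputed by chained equations, at least 100 times, and "these iterations will be combined according to Rubin's (1987) rules". A pattern-mixture sensitivity analysis follows.

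The section gives no reference distribution for the pooled test, no small-sample adjustment and no pooling procedure.

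**The concern.** Once one aided score is missing, the Intent to Treat result is the pooled one, and the only guidance on its reference distribution is the 1987 citation. The df in those rules depend on the number of imputations and the fraction of missing information. They treat the complete-data df as infinite. That is harmless in a large trial, but here the crossover contrast has about 42 df.

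With 100 or more imputations and little missing information, the 1987 df become very large and the test is in effect a z test. An incomplete trial would then face a lower critical value than the same trial with every score observed. The error always favours declaring non-inferiority, and the study is meant to support a 510(k) application.

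**Working it through.** **1. Inputs from section 9.** One-sided alpha 0.025; margin -12.5; assumed difference -5.0, so the distance to the margin is 7.5; SD of the difference 14; 40 evaluable and 44 enrolled subjects; two sequences; m = 100 imputations as the stated minimum. *Assumed, because the documents give none:* the relative increase in variance from missing data (r), the missingness pattern and the within-subject correlation.

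**2. The plan's own figure.** Normal formula: n = [14 × (1.960 + 1.282) / 7.5]² = 36.6, so 37. With a noncentral t on n - 2 df, power is 0.903 at n = 39 and 0.910 at n = 40. The stated 40 for 90% power is reproduced, with a little to spare.

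**3. Complete-data reference.** 44 - 2 = 42 df; critical value 2.018.

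**4. 1987 reference.** df = (m - 1)(1 + 1/r)² = (m - 1)/λ², with λ = r/(1 + r). For r = 0.10: λ = 0.0909 and df = 99 × 11² = 11,979.

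**5. Barnard-Rubin reference.** Observed-data df = (43/45) × 42 × (1 - λ). For r = 0.10 this is 36.5. Combined with the 1987 df: 1/(1/11,979 + 1/36.5) = 36.4.

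| r (assumed) | 1987 df | critical value | Barnard-Rubin df | critical value | ratio |
|---|---|---|---|---|---|
| 0.02 | 257,499 | 1.960 | 39.3 | 2.022 | 1.032 |
| 0.05 | 43,659 | 1.960 | 38.2 | 2.024 | 1.033 |
| 0.10 | 11,979 | 1.960 | 36.4 | 2.027 | 1.034 |
| 0.20 | 3,564 | 1.961 | 33.1 | 2.034 | 1.038 |

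In simulations with 2 or 4 of 44 subjects affected, the mean r was 0.03 to 0.11, so the first three rows are the relevant ones. Four subjects is about the plan's attrition ceiling (10% of 44 is 4.4).

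**6. Analytic size.** The tail beyond 1.96 is 0.0283 for a t with 42 df, 0.0285 with 40 df and 0.0288 with 36.4 df. These are approximations: they treat the pooled statistic as an exact t.

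**7. Simulated size.** The pooled AB/BA contrast was simulated at the margin with 44 subjects, regression imputation and m = 100.

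| Setting (assumed) | 1987 df | Barnard-Rubin df |
|---|---|---|
| Imputation from sequence, unaided score and period 1; 2 or 4 subjects missing scores; correlation 0.3, 0.6, 0.8; 40,000 trials each | 0.0263 to 0.0276 | 0.0227 to 0.0241 |
| Imputation from sequence and period 1, with and without the unaided score; 1, 2 or 4 visit-4 scores missing; correlation 0.3 to 0.7; 30,000 trials each | 0.0266 to 0.0291 | 0.0232 to 0.0257 |
| Imputation model including sequence; 4 visit-4 scores missing; correlation 0.3, 0.5, 0.7; 30,000 trials each | 0.0284, 0.0285, 0.0292 | 0.0248, 0.0245, 0.0248 |

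The Monte Carlo standard error is about 0.0006 to 0.0007 in the first two rows. In the first row's runs, the complete-case t test gave 0.0240 to 0.0249.

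**8. Effect on the limit.**
- Changing only the critical value at 42 df: (2.018 - 1.960) × 14/√44 = 0.058 × 2.11 = 0.12 points.
- At r = 0.10 the pooled SE is 2.11 × √1.10 = 2.21, and the shift is (2.0274 - 1.9602) × 2.21 = 0.15 points.
- Non-inferiority then needs an estimate above -12.5 + 1.9602 × 2.2136 = -8.16 with the 1987 df, or above -12.5 + 2.0274 × 2.2136 = -8.01 with the small-sample df. Only estimates between these two change the conclusion. If the true difference is -5.0, about 1% of trials fall there (normal approximation).

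**The case against.** **The plan never writes out a df formula.** This is true. A statistician could pool estimates and variances by Rubin's rules, supply the complete-data df and claim to have followed the plan. A reader might infer that the sponsor deliberately chose large-sample df; the text does not show that. What stands is that the plan cites one specific set of rules, those rules carry their own df, and nothing in section 9 modifies them. At best, two critical values remain open until the data are seen.

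**The problem is conditional.** This also stands. With all aided scores observed there is nothing to pool, and the GLM or MIXED contrast uses its own t reference. A reader might infer that the trial as designed runs at about 0.0285. The documents do not support an unconditional figure. That value is also just the tail of a t with 40 df beyond 1.96, and the simulated size is sometimes lower.

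**The effect is small.** The excess error is about 0.001 to 0.004, and the limit moves by 0.12 to 0.15 points against a 12.5-point margin. This limits the severity but does not remove the point, because the stated alpha is missed in a known direction.

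**The secondary endpoint.** A reader might carry the same error rate over to dB SNR loss. The same pooling applies, but the plan gives no non-inferiority margin for that endpoint, so no type I error can be computed.

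**Conclusion.** The point holds as a minor one. If at least one aided score is missing and the 1987 rules are followed literally, the primary test uses a critical value of about 1.96 where about 2.02 to 2.03 is appropriate. Its one-sided size is then roughly 0.026 to 0.029 instead of 0.025. The range reflects assumptions about how many scores are missing, the within-subject correlation and the imputation model, none of which the documents give. In the tabulated simulations every setting exceeded 0.025 with the 1987 df, while Barnard-Rubin df brought the size to between 0.0227 and 0.0257. The non-inferiority conclusion would change only for an estimate within about 0.15 points of the decision boundary.

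**What to change.** In section 9, replace the pooling sentence with wording to this effect: point estimates and variances are combined by Rubin's rules; tests and confidence limits after imputation use the Barnard-Rubin small-sample degrees of freedom, with complete-data degrees of freedom equal to the number randomized minus 2 (42 for 44 subjects). Apply the same rule to the dB SNR loss analysis and to the pattern-mixture sensitivity analyses.

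The cost is one sentence, the complete-data df supplied at pooling, and a confidence half-width about 3% wider. No extra subjects are needed: 40 complete pairs on 38 df give 91% power under the plan's own assumptions.

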## **10 Investigation Duration**

The total expected duration of the clinical investigation is six months, with the expected duration for each participant to be 5 weeks.

## **11 Data handling and management**

Electronic or paper based CRFs will be used to capture the participants' answers to the APHAB questionnaire. If electronic, the questionnaire will be available in the EDC system and the participant will be able to read question and choose answer. If paper based, the participant will answer each question and the results will be transferred to the EDC by the investigator. All CRFs are kept current to reflect the subject's status at each phase during the course of study. Participants cannot be identified in the CRF by name or initials and birth date but an appropriate coded identification is used. All study team members are authorized for the CRF entries and it is assured that any authorized person can be identified both for pCRFs and eCRFs. If pCRFs are used, the investigator's initials and subject ID are documented and data are entered into an electronic file for analysis by the respective investigator and data will be monitored by the assigned monitor. In case of a self-evident corrections, either the subject does it by himself or the investigator undertakes the correction by crossing out the word/sentence with a single horizontal line and by adding the correction including his personal identifier and the date. The results for the QuickSiN objective measure will be taken from the computer used to complete the test and imported into the EDC system or transferred via an excel or csv file. Real Ear Measurements will be imported from the verification system and stored as an excel file. The EDC system is password protected and has an audit trail. Only the PI and sub-investigators will have access for inputting data.

## **12 Amendments to the CIP**

Any necessary amendments to the CIP will be communicated to the study manager/sponsor. A new version of the CIP will be written, with the necessary changes and justification, and the PI will be trained on the amendments. The amended CIP will go through the approval process and necessary signatures obtained from the study manager/sponsor, PI, and statistician. The amended CIP will be uploaded to the eQMS system as an additional revision.

## **13 Deviations from clinical investigation plan**

Deviations from the CIP to protect the rights, safety and well-being of human participants under emergency circumstances may proceed without prior approval of the sponsor and the EC – such deviations will be documented and reported to the sponsor representative (Study Manager) and the EC as soon as possible. Apart from that the investigator is not allowed to deviate from this CIP unless that deviation does not influence the investigation data.

## **14 Device accountability**

Study devices must be returned to Sonova at the completion of the study. Sonova, in its capacity as sponsor, will maintain a log of all investigational devices, including the date of shipment from Sonova to the site, serial number, receiving study site, and date returned to Sonova.

The site will maintain a log of the devices provided by Sonova, including the date of receipt, serial number, date of fitting, participant identification, date of return to site by participant, and date returned to Sonova. Sonova will provide each site a template with which to record such information.

If a device needs to be replaced due to a device deficiency, the PI or sub-investigator will add the new device serial number, date of receipt, and date of return of the defective device on the Device Accountability Log.

In the case of a device deficiency, the Adverse Event-Device Deficiency form will be completed by the study manager and the PI or sub-investigators together.

## **15 Informed consent process**

Informed consent will be obtained from participants prior to any study participation in accordance with the IRB guidelines. The participants will be granted sufficient time to read through the consent in full and ask any questions they have before signing. After the participant signs the consent form, the researcher will sign and provide a copy to the participant. This process will take place in a private office located at the study site.

Informed Consent will only be obtained by investigation participants who can provide informed consent themselves before enrollment.

## **16 Adverse events, adverse device effects and device deficiencies**

Device deficiencies and all **adverse events (AE)** including all **serious adverse events (SAE)** are collected, fully investigated and documented in the source document and appropriate case report form (CRF) during the entire investigation period, i.e. from participant's informed consent until the last protocol-specific procedure, including a safety follow-up period (ISO-14155, 2020). Documentation includes dates of event, treatment, resolution, assessment of seriousness and causal relationship to device and/or investigation procedure.

Information on AEs is systematically collected during the regular investigation visits, and phone calls (if applicable).

The investigator(s) will follow-up on a biweekly basis with any participant experiencing an AE until either a) the participant reports resolution of the AE or b) 8 weeks have passed since the participant's final visit. If, however, the participant's condition worsens throughout the 8 week follow-up period, the investigator will continue to follow-up biweekly until the AE is resolved or the participant's condition stabilizes over an 8 week period.

The reporting of Serious Adverse Events and Device Deficiencies follows the Regulation (EU) 2017/745 and the MDCG 2020-10/1 Safety Reporting in Clinical Investigations of Medical Devices under Regulation (EU) 2017/745.

The causality assessment of the SAE will be conducted according to MDCG 2020-10/1 Safety Reporting in Clinical Investigations of Medical Devices under Regulation (EU) 2017/745.

## **17 Vulnerable populations**

This investigation will not include any vulnerable populations.

## **18 Suspension or premature termination of the clinical investigation**

The study will be terminated if the majority of the participants are not able to wear the devices for the study visit.

The study will be terminated if the participants or researchers are exposed to safety risks other than those outlined in this document.

The study may be terminated in the event natural disasters, widespread outbreak of illness, compromised structure of the investigation site, etc. that would make continuation of the study

impossible or impractical. The study will be suspended within 5 days of determination that the study or device put participants at an unreasonable risk.

If a participant is suspended, terminated, or withdraws from the study, their data can be traced with their unique study identification number.

According to the FDA, follow-up is required for participants who experience Serious Adverse Events. Follow up will be conducted by the study manager and/or the PI until the nature of the event is resolved.

## **19 Publication policy**

The clinical investigation will be registered in [clinicaltrials.gov](https://clinicaltrials.gov), a publicly accessible database, as required by U.S. regulations.

The results of the clinical investigation will be published on [clinicaltrials.gov](https://clinicaltrials.gov) no later than one calendar year following the final participant appointment.

An internal report of the results of this investigation will be completed and uploaded to eQMS.
